10.3.7. Secondary Objectives

10.3.7.1. Objective: To compare the annualized bleeding rate for major, life threatening, and joint bleeds.

ABRs for other bleeding outcomes described in [Table 6](#) (major bleeds, life-threatening bleeds and joint bleeds) will also be compared between the Roctavian Cohort and SoC Cohort after PS adjustment. The analysis approach will be consistent with the primary objective (see Section [10.3.6](#)) regarding PS adjustment approach, analysis of the full follow-up time along with annual increments, as well as measurement of treatment effect.

10.3.7.2. Objective: To compare the proportion of participants with zero bleeds for treated, major, life threatening, and joint bleeds.

Proportion of participants with zero bleeding events for all bleeding outcomes described in Table 6 will be compared between the Roctavian Cohort and SoC Cohort after PS adjustment, generally consistent with the analysis approach for ABRs (see Section 10.3.6 above) regarding PS adjustment approach, analysis of the full follow-up time along with annual increments, as well as, start of bleed follow-up and censoring reasons.

Differing from the approach for ABRs, analyses of the proportion of participants with zero bleeding will only include those participants with follow-up for the full time over which the proportion is calculated. Additionally, the measurement of treatment effect for these analyses will be the relative risk and 95% confidence interval between participants in the Roctavian Cohort and SoC Cohort having zero bleeding events.

10.3.7.3. Objective: To compare the use of hemostatic medications.

The use of hemostatic medications will be compared between the Roctavian Cohort and SoC Cohort after PS adjustment, generally consistent with the analysis approach for ABRs (see Section 10.3.6 above) regarding PS adjustment approach, and analysis of the full follow-up time along with annual increments. Comparisons will be made regarding the variables in Table 7.

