Joint ABR	Yes (calculated)	
 Occasion Localization Date of bleed 	
 Number of joint bleeding events per year Calculate ABR using number of bleed events within the relevant time period (≥ 1 year of follow-up, ≥ 2 years of follow-up, ≥ 3 years of follow-up, all available follow-up) Joint bleeds are defined as treated bleeds (see definition above) and based on localization of bleed 
 Note: a bleeding event is captured if occasion for therapy is spontaneous bleeding/hemorrhage (regardless of severity) Calculate annualized metric of the number of bleeding events by dividing the number of bleeds by the number of days in the relevant time period, multiplied by 365.25 	
 ≥ 1 year ≥ 2 years ≥ 3 years All available follow-up
% Zero treated bleeds	Yes (calculated)	
 Therapy scheme Occasion Start of reporting period End of reporting period 	
 % Of participants with zero treated bleeds calculated based on treated bleeding No bleeding events captured within the reporting period start and stop dates The number of participants within the Cohort with zero treated bleeds is divided by the total number of participants in the Cohort See definition for treated bleed above to be used to derive this variable 	
 ≥ 1 year ≥ 2 years ≥ 3 years All available follow-up
% Zero major bleeds	Yes (calculated)	
 Occasion Severity Start of reporting period End of reporting period 	
 % Of participants with zero major bleeds calculated based on major bleeding No bleeding events captured within the reporting period start and stop dates The number of participants within the Cohort with zero major bleeds is divided by the total number of participants in the Cohort See definition for major bleed above to be used to derive this variable 	
 ≥ 1 year ≥ 2 years ≥ 3 years All available follow-up

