7.9.4.2. Proportion of Participants with Zero Bleeds

Population	Measurement Period
All participants	≥1 year of follow-up, ≥2 years of follow-up, ≥3 years of follow-up, all available follow-up

For interim and analyses at fixed timepoints, only those with specified amounts of follow-up will be included	
---	--

The proportion of participants who had no bleeding events of each of the following types will be reported and compared between the Roctavian and SoC Cohorts: treated bleeds, major bleeds, life threatening bleeds, and joint bleeds. The approach will be generally consistent with the analysis approach for ABRs (see Section 7.9.3) regarding the adjustment approach (IPTW), analysis of the full follow-up period along with annual increments and start of follow-up period.

The binary outcomes will be analyzed using propensity score IPTW weighted log binomial regression models. The main predictor of interest is the treatment effect (Roctavian vs. SoC), other imbalanced covariates after propensity score adjustment may be included in the model as necessary. The risk ratio (relative risk), corresponding 95% CIs and p-values will be reported.

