Acronyms: SoC: standard of care

Note: Std. diff. examines the balance of covariate distribution between groups, with a value >0.1 indicating some imbalance between groups and >0.25 indicating poor balance.

Table 8 IPTW-Adjusted Logistic Regression Model of Participants with Zero Bleeds for the Overall Timeframe, Roctavian and SoC Cohorts

Unadjusted Logistic Regression Model

Measures	Risk Ratio	95% Confidence Limits		p-value
		Lower Limit	Upper Limit	
Zero treated bleeds				
Roctavian (vs. SoC)	0.00	0.00	0.00	0.0000
Zero major bleeds				
Roctavian (vs. SoC)	0.00	0.00	0.00	0.0000
Zero life-threatening bleeds				
Roctavian (vs. SoC)	0.00	0.00	0.00	0.0000
Zero joint bleeds				
Roctavian (vs. SoC)	0.00	0.00	0.00	0.0000

Adjusted Logistic Regression Model (if conducted)

Measures	Risk Ratio	95% Confidence Limits		p-value
		Lower Limit	Upper Limit	
Zero treated bleeds				
Roctavian (vs. SoC)	0.00	0.00	0.00	0.0000
Zero major bleeds				
Roctavian (vs. SoC)	0.00	0.00	0.00	0.0000
Zero life-threatening bleeds				
Roctavian (vs. SoC)	0.00	0.00	0.00	0.0000
Zero joint bleeds				
Roctavian (vs. SoC)	0.00	0.00	0.00	0.0000

Data source: DHR from the start of data collection accompanying the application to approximately 6 months prior to the date of the final report required by the G-BA resolution for AbD
 Acronyms: SoC: standard of care

Table 9 Hemostatic Medication Use for Roctavian and SoC Cohorts

Measures	Unadjusted										After IPTW									
	Roctavian Cohort		SoC Cohort		FVIII Sub-Cohort		Emicizumab Sub-Cohort		p-value (Roctavian vs. SoC)	Std. Diff. (Roctavian vs. SoC)	Roctavian Cohort		SoC Cohort		FVIII Sub-Cohort		Emicizumab Sub-Cohort		p-value (Roctavian vs. SoC)	Std. Diff. (Roctavian vs. SoC)
	N=		N=		N=		N=				N=		N=		N=					
	N	(%)	N	(%)	N	(%)	N	(%)	N	(%)	N	(%)	N	(%)	N	(%)	N	(%)		
Participants with any hemostatic medication use																				
Overall	0	0.0%	0	0.0%	0	0.0%	0	0.0%			0	0.0%	0	0.0%	0	0.0%	0	0.0%		
≥1 year follow-up	0	0.0%	0	0.0%	0	0.0%	0	0.0%			0	0.0%	0	0.0%	0	0.0%	0	0.0%		
≥2 years follow-up	0	0.0%	0	0.0%	0	0.0%	0	0.0%			0	0.0%	0	0.0%	0	0.0%	0	0.0%		
≥3 years follow-up	0	0.0%	0	0.0%	0	0.0%	0	0.0%			0	0.0%	0	0.0%	0	0.0%	0	0.0%		
Participants with hemostatic medication use for bleeds or short-term prophylaxis																				
Overall	0	0.0%	0	0.0%	0	0.0%	0	0.0%	0.0000	0.00	0	0.0%	0	0.0%	0	0.0%	0	0.0%	0.0000	0.00
≥1 year follow-up	0	0.0%	0	0.0%	0	0.0%	0	0.0%	0.0000	0.00	0	0.0%	0	0.0%	0	0.0%	0	0.0%	0.0000	0.00

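### The SAP adds a whole-cohort zero-bleed comparison over unequal follow-up, against the protocol's full-follow-up rule; it favours the cohort observed for less time, mainly under the hypothetical estimand

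*Protocol*

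**What the plan says.** The protocol separates the two bleeding measures. Section 7.2.5.1 lets bleeding rates use varying observation times but ties the zero-bleed share to a fixed period. Section 10.3.7.2 makes this a rule: zero-bleed analyses "will only include those participants with follow-up for the full time over which the proportion is calculated".

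The SAP, bound in the same file, says several things:

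- **Section 7.4.3, Table 5**, for treated bleeds: "The number of participants within the Cohort with zero treated bleeds is divided by the total number of participants in the Cohort". The entries for major, life-threatening and joint bleeds are parallel. All available follow-up is one of the four listed timepoints.
- **Section 7.9.4.2** takes all participants as the population and gives the periods as "≥1 year of follow-up, ≥2 years of follow-up, ≥3 years of follow-up, all available follow-up". Its restriction reads: "For interim and analyses at fixed timepoints, only those with specified amounts of follow-up will be included". The text asks for "analysis of the full follow-up period along with annual increments and start of follow-up period", and for the model it says: "The binary outcomes will be analyzed using propensity score IPTW weighted log binomial regression models".
- **Section 7.9.4.3**, on hemostatic medication, refers back to the zero-bleed analyses as restricted to participants with complete follow-up for the period, which is the protocol's rule.
- **Section 12.1**: shell Table 7 reports the overall period and the 1-, 2- and 3-year versions. The only shell for model results, Table 8, is titled "IPTW-Adjusted Logistic Regression Model of Participants with Zero Bleeds for the Overall Timeframe, Roctavian and SoC Cohorts".

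Under the hypothetical estimand (Protocol 10.3.2.3, SAP 7.2.3), Roctavian follow-up starts no earlier than 5 weeks after infusion, later for some, and is censored when prophylaxis resumes. SoC follow-up starts at index. SAP 12.1 says the shells will be adjusted and populated for this estimand too.

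**The concern.** A programmer following Protocol 10.3.7.2 and one following SAP Table 5 would use different denominators for the same four secondary endpoints. SAP 7.9.4.3 sides with the protocol, so the SAP also disagrees with itself.

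The choice affects the result. A participant observed for one year has had less opportunity to bleed than one observed for three, so having no bleeds over whatever time was available is a different outcome for each. The negative binomial model for bleeding rates handles this with log follow-up time as an offset (SAP 7.9.3); the log-binomial model has no stated counterpart. If one cohort is observed for less time, it will look bleed-free more often even when the true rates are equal. Under the hypothetical estimand, the late start and the censoring at resumption both shorten Roctavian time, so the risk ratio would be pushed in Roctavian's favour.

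**Working it through.** **Inputs.** Protocol 10.1 and SAP 7.6 give treated-bleed rates of 3 per year (SoC) and 0.85 per year (Roctavian), and overdispersion φ = 1.5. Follow-up is 3 years from index (SAP 7.3.3). Neither document gives a follow-up distribution, a withdrawal rate or a rate of return to prophylaxis, so those are assumptions below.

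**The plan's own figure.** No figure is stated for the zero-bleed endpoint. The same inputs do drive the sample size, so I checked them there. With the SAP 7.6 formula:

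- V₁ = 1/3 + 1/(0.2 × 0.85) + 1.2 × 1.5/0.2 = 15.22
- V₀₂ = 1.1²/(0.5 × 0.2 × 3.17) + 9 = 12.82
- N₁ = (1.960√12.82 + 0.842√15.22)² / (ln 0.5 − ln(0.85/3))² = 328.8

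This gives 329 SoC and 66 Roctavian, 395 in total against the stated 397. The inputs are being read as the plan intends.

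**Chance of no bleeds.** For a negative binomial count at rate λ over t years, P₀(t) = (1 + φλt)^(−1/φ). With φ = 1.5:

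| Rate per year | t = 1 | t = 1.5 | t = 2 | t = 3 |
|---|---|---|---|---|
| 0.85 | 0.578 | 0.490 | 0.430 | 0.350 |
| 3 | 0.321 | 0.255 | 0.215 | 0.168 |

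**Spurious risk ratio.** Give both cohorts the same rate, so the true ratio is 1. Observe SoC for 3 years. In the Roctavian cohort, let a fraction f be censored at 1.5 years and the rest be observed for 3 − 5/52.18 = 2.90 years. Then

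RR = [f·P₀(1.5) + (1 − f)·P₀(2.90)] / P₀(3).

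For λ = 3 and f = 0.25: (0.25 × 0.255 + 0.75 × 0.172)/0.168 ≈ 1.145 before rounding of the inputs.

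| f (assumed) | λ = 0.85 | λ = 1.5 | λ = 3 |
|---|---|---|---|
| 10% | 1.06 | 1.06 | 1.07 |
| 25% | 1.11 | 1.13 | 1.15 |
| 50% | 1.21 | 1.24 | 1.27 |

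Dispersion matters. At f = 25% and rates from 0.85 to 3, the range is 1.06–1.07 if φ = 3 and 1.26–1.51 if φ = 0.5.

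**At the planning rates.** Over an equal 3 years the ratio is 0.350/0.168 = 2.08. With 25% of the Roctavian cohort censored as above it becomes 2.08 × 1.113 = 2.32.

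**Rarer bleed types.** At an assumed 0.05 per year, P₀ is about 0.953 at 1 year and 0.911 at 2 years. Even a twofold gap in follow-up then gives only about 1.05.

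**The case against.** Several stronger readings are tempting, and the documents do not support them.

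- A reader might infer that the SAP models only the overall version. That rests on the title of shell Table 8, and the bleeding-rate shell (Table 6) carries the same overall-timeframe label. The text of 7.9.4.2 covers annual increments as well, and shell Table 7 reports the 1-, 2- and 3-year proportions with weighted p-values. What stands is that no model shell exists for those windows.
- A reader might infer that every interim analysis is affected. SAP 7.9.4.2 restricts interim and fixed-timepoint analyses by follow-up, and SAP 7.9.6 limits the 18-month comparisons to participants with at least one year.
- A reader might infer equal harm under both estimands. Under treatment policy both cohorts run from index for up to 3 years, and Protocol 8.2 does not anticipate loss to follow-up.
- A reader might assume mean follow-up of 1 versus 2 years and obtain 0.321/0.215 = 1.49. The arithmetic is right, but nothing in the documents points to such a gap.

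It can also be said that the Table 5 denominator is a generic definition of a percentage, that SAP 7.9.4.3 shows the intent, and that Protocol 10.3.7.2 itself plans a full-follow-up analysis. All true, but the protocol attaches its restriction to that analysis, and SAP 7.9.4.2 does not carry it over to the all-available-follow-up period. SoC participants who later receive Roctavian are censored under the hypothetical estimand, which shortens SoC time and works the other way. Finally, these are secondary endpoints with nominal p-values, and the primary model does account for follow-up time.

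**Conclusion.** The point holds in limited form and is worth correcting. The whole-cohort, all-available-follow-up proportion contradicts Protocol 10.3.7.2 and SAP 7.9.4.3. Analysed without a time term, it favours the cohort observed for less time.

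The main exposure is the hypothetical estimand. There the spurious risk ratio for treated bleeds is about 1.06 to 1.27 when 10% to 50% of Roctavian participants are censored at 1.5 years. These figures assume φ = 1.5, equal true rates, complete 3-year follow-up in SoC and an invented censoring pattern, so they show scale and do not predict a result. The bias would be smaller for major and life-threatening bleeds if those are rare, and small at the final treatment-policy analysis unless withdrawal differs between cohorts.

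**What to change.** Align SAP Table 5, SAP 7.9.4.2 and shell Tables 7 and 8 with the protocol rule:

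1. Define zero-bleed proportions over fixed windows, with a denominator of participants observed for the whole window.
2. Add model shells for those windows.
3. Drop the unadjusted all-available-follow-up comparison, or keep it labelled descriptive with no risk ratio or p-value.
4. For the hypothetical estimand, count windows from the start of analytical follow-up and use only windows that can be completed. With a start at least 5 weeks after index and an end at index plus 3 years, at most 2.90 years are available, so a 3-year window cannot be met.
5. Report how many participants are excluded from each window because they resumed prophylaxis. The full-window rule removes the unequal-time problem but selects those who stayed off prophylaxis, and readers need to see how many were lost.

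A complementary log-log model with log follow-up as offset is not a simple way to keep the overall comparison: it is exact only without overdispersion, and the plan assumes 1.5.

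The cost is wording and shells; no new data are needed. Protocol 10.3 has the SAP finalized before the first data cut, so there is a natural point to do it.

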Age at first FVIII therapy administration	Age of first FVIII administration	✓	--	At enrollment	Description of cohorts Derived based on date of first FVIII therapy administration and year of birth record in DHR, unless date of administration is recorded as 'unknown'.
History of or current inhibitors	Any history of or current inhibitors	✓	At index or any time prior to index	At enrollment & ongoing	Exclusion criteria Based on recording of the DHR variables for inhibitors developed before the patient started treatment at the current treatment center, positive inhibitor tests after enrollment in the DHR, or use of immune tolerant therapy (ITT). Exclusion will be based upon either 2 positive inhibitor tests (regardless of occurrence before or after enrollment in DHR) or 1 positive inhibitor tests (regardless of occurrence before or after enrollment in DHR) and use of ITT. Exclusion criteria additionally confirmed at time of enrollment based on DHR field

Variable	Description	Captured in DHR	Time period for Analysis	Entry into DHR	Operational notes including Relevant Data Fields in DHR
					confirming that the participant fulfills the AbD inclusion/exclusion criteria.
von Willebrand Factor	von Willebrand factor level	✓	At index or any time prior to index	At enrollment into the AbD	Potential variable for inclusion in the propensity score, to be determined based on statistical association
Target joints	Presence of target joints	✓	At index and/or during baseline	Ongoing	
Description of cohorts.
 
Presence of a target joint will be derived based on therapy usage recorded in the DHR for bleeding with the bleeding location identified as ‘target joint’. Number and location of target joints will be based on location (shoulder, elbow, hip, knee, ankle, or other) and side (left, right, not applicable, or unknown) of bleeds identified as ‘target joint’. For example, if a target joint bleeds are recoded at the same location on both sides (eg, a target joint bleed at the left ankle and a separate target joint bleed at the right ankle), this will be counted as 2 separate target joints. If the target joint location is ‘other joint’ or the side of bleeding is ‘not applicable or unknown’, the number of target joints identified from the bleed will be counted as 1 target joint.
 
Note: Target joint is defined based on the discretion of the physician recording the data in the DHR and does not necessarily adhere to the ISTH definition for a target joint.

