Adverse events leading to hospitalization and/or death	Medical event leading to hospitalization and/or death	✓	Follow-up (inclusive of index)	Ongoing	
The DHR captures information on medically relevant events including allergic reactions, thromboembolic events, thrombotic microangiopathy, malignant neoplasm, autoimmune disease, sensory paresthesia, infusion/hypersensitivity reaction, complications of immunosuppression and other with a free text field to specify the other category. For each event, the connection to hemophilia treatment (yes/no/unknown) is also recorded, along with serious consequences due to the event (hospitalization, death, none or unknown).
 
Event recorded as leading to hospitalization and/or death will be analyzed both for any reason (regardless of relation to hemophilia treatment) and related to hemophilia treatment. (See limitations of interpretation of events regardless of relationship to hemophilia treatment in Section 10.5).
 
Hospitalizations are defined as a participant having been admitted to the hospital for inpatient care, either to the inpatient ward or to the emergency room for observation and/or treatment that would not have been appropriate in the physician’s office or outpatient setting.

Variable	Description	Captured in DHR	Time period for Analysis	Entry into DHR	Operational notes including Relevant Data Fields in DHR
Targeted Adverse Events					
Development of FVIII inhibitors	Positive inhibitor tests and/or a positive test and the requirement for ITT	✓	Follow-up (inclusive of index)	Ongoing	Based on recording of the DHR variables for positive inhibitor tests after enrollment in the DHR, or use of immune tolerant therapy (ITT). See Table 4 and SAP for additional information on definition for positive inhibitors based on 2 positive tests or 1 test and use of ITT.
Thromboembolic events	Occurrence of a thromboembolic event related to treatment	✓	Follow-up (inclusive of index)	Ongoing	Derived based recording of medically relevant event of thromboembolic event in the DHR that has been identified as connected to hemophilia treatment. Occurrence of thromboembolic events regardless of relationship to treatment will also be described, but not compared. (See limitations of interpretation of events regardless of relationship to hemophilia treatment in Section 10.5)

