7.3.5.3. Inclusion/Exclusion Criteria Variables

Table 2 outlines the variables and operational definitions of the inclusion/exclusion criteria.

Table 2: Inclusion/Exclusion Criteria Variables

Variable	Captured in DHR	DHR data field name	Operational definition/description
Clinical trial participation	Yes	
 • Participation in clinical trial • Current participation in clinical trial • Name of the clinical trial 	
 • In the last 12 months before index • No (exclude participant if yes) • Clinical trial name (free text field) to be utilized to specifically exclude interventional trials, if feasible; If not feasible, any clinical trial will be excluded • Participation in AbD and/or non-interventional studies of Roctavian will not result in exclusion • Exclusion criteria confirmed at time of enrollment based on DHR field confirming that the participant fulfills the AbD inclusion/exclusion criteria
History of Inhibitors (ever)	Yes	
 • Diagnosis • Inhibitor tests against FVIII/FIX positive in this reporting period • Occasion • Positive/negative result 	
 • Yes/No • Based on any recording of the DHR variables for inhibitors developed before the participant started treatment at

Variable	Captured in DHR	DHR data field name	Operational definition/description
			
the current treatment center, positive inhibitor tests after enrollment in the DHR, or use of immune tolerance therapy (ITT)
 
 Exclusion will be based upon either 2 positive inhibitor tests (regardless of occurrence before or after enrollment in DHR) or 1 positive inhibitor tests (regardless of occurrence before or after enrollment in DHR) and use of ITT Use of ITT will be identified if occasion = "ITT" Exclusion criteria additionally confirmed at time of enrollment based on DHR field confirming that the participant fulfills the AbD inclusion/exclusion criteria.
Severe HA	Yes	
 Diagnosis Hemophilia severity 	
 Severe (exclude participant if moderate, mild, or subclinical) Inclusion criteria additionally confirmed at time of enrollment based on DHR field confirming that the participant fulfills the AbD inclusion/exclusion criteria

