Hemophilia-related death	Yes	
 Reason for resignation Cause of death Date of retirement 	
 If reason for resignation from DHR is "deceased" and cause of death is captured as "hemophilia-related" 	All available follow-up
AEs leading to hospitalization and death	Yes	
 Medically relevant events in this reporting period Relation to hemophilia treatment Serious consequences due to relevant events 	
 Identified if serious consequences due to relevant events = "hospitalization" or "death"² Events will be analyzed both for any reason (regardless of relation to hemophilia treatment) and related to hemophilia treatment 	All available follow-up
Development of FVIII inhibitors	Yes (calculated)	
 Inhibitor tests against FVIII/FIX positive in this reporting period Date of the inhibitor test Titer Test assay used 	
 If inhibitor tests against FVIII/FIX were performed during the reporting period, participants with a positive test will be identified Based on any recording of the DHR variables for inhibitors developed during the reporting period, positive inhibitor tests during the reporting period, or use of ITT (occasion = "ITT") Titer (BU/ml) 0.0-1000.0 	All available follow-up

Variable	Captured in DHR	DHR data field name(s)	Operational definition and calculation of outcome measures	Timepoints for data collection
		
 Occasion 		
Thrombo-embolic events	Yes	
 Other relevant event Relation to hemophilia treatment 	
 Thromboembolic events connected to hemophilia treatment will be identified if other relevant event = “thromboembolic event” and relation to hemophilia treatment = “yes” 	All available follow-up

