 - In addition to variables that are not feasible to capture in an observational registry, the non-interventional nature of the study reflecting a range of real-world practice in Germany could introduce confounding that cannot be fully addressed with PS or specific applications of the PS (e.g. matching). For example, PwSHA are recommended to be treated with hemostatic prophylaxis, though a small portion of the severe hemophilia A population in Germany may still be utilizing an on-demand treatment regimen. Persons utilizing an on-demand regimen are likely to have a higher baseline bleeding rate, as prophylaxis is associated with reduced bleeding events. All persons administered commercially available Roctavian are expected to have received hemostatic prophylaxis treatment for at least 12 months by the time that a participant will be treated with Roctavian gene therapy. If persons treated with an on-demand regimen for part of the baseline period enroll into the SOC Cohort, these participants may have outlier propensity scores which may not be able to be matched. The proportion of on-demand participants in the SOC Cohort, as well as impact of these participants on the analysis will be discussed in interim and final reports.
- **Loss to follow-up:** Participant retention through the end of the expected observation period will be monitored carefully and attempts will be made to obtain follow-up data from participants who discontinue treatment. However, some participants may have fewer than three years of follow-up data available. Participants in the SoC Cohort are expected to have follow-up twice per year whereas participants in the Roctavian Cohort may have more frequent touchpoints due to them being on a newer treatment.
- **Missing data:** The data leveraged for this study are dependent on physicians and hospitals to accurately record each event. Methods are in place for handling missing data (Section 9.7.5) and a sensitivity analysis of missing data will be conducted.
- **Heterogeneity of SoC:** The assumption of treatment consistency specifies that there is no ambiguity defining a treatment. This assumption is also known by the term "treatment variation irrelevance". For this study, the two compared treatment groups are Roctavian versus SoC with SoC being different for various participants. Therefore, treatment consistency is approximately

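### The SAP's outcome row for FVIII inhibitor development omits the confirmation rule that protocol Table 8 refers to, so an unconfirmed positive test, or ITT alone, would count as an event.

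*Protocol*

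**What the plan says.** **Protocol Table 8 (Section 7.2.5.7).** The short description of the outcome is loose: "Positive inhibitor tests and/or a positive test and the requirement for ITT". The operational note begins with recordings of positive tests or use of ITT. It closes by pointing to Table 4 and the SAP for the "definition for positive inhibitors based on 2 positive tests or 1 test and use of ITT".

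**Protocol Table 4 (Section 7.2.3).** The history-of-inhibitors row lists the source fields and then sets the rule for exclusion: two positive tests, or one positive test together with ITT.

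**SAP Table 2 (Section 7.3.5.3).** The same rule is kept for the baseline exclusion: "Exclusion will be based upon either 2 positive inhibitor tests", or one positive test and use of ITT.

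**SAP Table 5 (Section 7.4.3).** The outcome row has three bullets. The first is "If inhibitor tests against FVIII/FIX were performed during the reporting period, participants with a positive test will be identified". The second bases the variable on any inhibitor recording, positive tests in the reporting period, or use of ITT. The third is "Titer (BU/ml) 0.0-1000.0", a range without a positivity cut-off. None of them asks for confirmation.

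**Use of the outcome.** Protocol Section 10.3.7.5 and SAP Section 7.9.4.5 compare the safety events between cohorts. SAP shells 15 and 16 give inhibitor development its own rows, with p-values and a regression estimate.

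**The concern.** Protocol Section 7.2.2 says that operational definitions are held in the SAP, so SAP Table 5 is the text a programmer would follow. A programmer working from protocol Table 8 and one working from SAP Table 5 could produce different event counts for the same endpoint.

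The SAP is also inconsistent with itself. A single unconfirmed positive before index does not meet the Table 2 inhibitor definition, yet the same result after index is an inhibitor event under Table 5.

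Inhibitor development is a named targeted adverse event and the Roctavian Cohort is small. Each misclassified participant moves the crude proportion by 1/70 = 1.4 percentage points in the Roctavian Cohort and by 1/330 = 0.3 points in the SoC Cohort.

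There may also be a differential effect. A count of single positives rises with the number of tests done. SAP Section 7.10 expects SoC follow-up twice per year and adds that "participants in the Roctavian Cohort may have more frequent touchpoints due to them being on a newer treatment". If extra contacts bring extra inhibitor tests, false positives would accumulate faster in the Roctavian Cohort.

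**Working it through.** **Step 1: the definitions side by side**

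| Place | Purpose | Two positive tests | One positive plus ITT | One positive only | ITT only |
|---|---|---|---|---|---|
| Protocol Table 4 | exclusion | yes | yes | no | no |
| SAP Table 2 | exclusion | yes | yes | no | no |
| Protocol Table 8, closing reference | outcome | yes | yes | no | no |
| SAP Table 5, as written | outcome | yes | yes | yes | yes |

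The opening list of source fields is nearly the same in all four places. In the first three, the confirmation rule follows that list or is referred to. In SAP Table 5 it does not appear.

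**Step 2: illustration of what confirmation changes**

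The documents state no figure for this outcome, so there is nothing to reproduce. Assumptions, none of them from the documents:
- false-positive probability per test f = 0.2% to 2%, independent between tests;
- 6 tests per SoC participant over three years, that is, one at each twice-yearly visit;
- 12 tests per Roctavian participant, with 24 as a more extreme case.

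For k tests:
- P(at least one false positive) = 1 − (1 − f)^k
- P(at least two) = 1 − (1 − f)^k − k·f·(1 − f)^(k−1)

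For example, with f = 0.5% and k = 6: 1 − 0.995^6 = 2.96%. Subtracting 6 × 0.005 × 0.995^5 = 2.93% leaves about 0.04%.

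| f | One positive: 6 tests | 12 tests | Ratio | Two positives: 6 tests | 12 tests | Ratio |
|---|---|---|---|---|---|---|
| 0.2% | 1.2% | 2.4% | 2.0 | 0.006% | 0.03% | 4.4 |
| 0.5% | 3.0% | 5.8% | 2.0 | 0.04% | 0.16% | 4.3 |
| 1% | 5.9% | 11.4% | 1.9 | 0.15% | 0.62% | 4.2 |
| 2% | 11.4% | 21.5% | 1.9 | 0.57% | 2.3% | 4.1 |

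- At f = 0.5%, with cohorts of 70 and 330, the single-test rule gives about 4.1 falsely flagged Roctavian participants and 9.8 SoC participants. The two-test rule gives about 0.1 in each.
- The spurious risk difference at 12 v 6 tests is 1.2 to 10.1 points under the single-test rule and 0.02 to 1.7 points under the two-test rule.
- At 24 v 6 tests, the single-test ratio is 3.4 to 3.9.
- With equal testing in both cohorts, the false-positive risks are equal and there is no differential excess under either rule.

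**Step 3: what the confirmed rule does not do**

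It cuts the absolute number of false positives sharply. The ratio of false-positive risks between unequally tested cohorts goes up, from about 1.9–2.0 to about 4.1–4.4. Dependence on testing frequency therefore remains, and the number of tests has to be reported whichever rule is used.

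**The case against.** The strongest reply is that SAP Table 5 is an incomplete carry-over and not a deliberate rival rule. Its second bullet repeats the list of source fields used in SAP Table 2 and protocol Tables 4 and 8, and nothing in the SAP argues for a different outcome rule. Protocol Table 8 is itself loosely worded in its short description. This stands: an omission is the likelier explanation. The row as written would still be programmed without confirmation, and its first bullet refers to a single positive test.

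A reader might go further and infer that the comparison will be biased against Roctavian. The documents do not support that. The remark on contacts says only that they may be more frequent, it sits in a paragraph on loss to follow-up, and it does not mention inhibitor tests. Protocol Table 2 has inhibitor status recorded as observed after index and sets no testing schedule for either cohort.

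A reader might also take the percentages above as the expected size of the problem. They rest on an assumed error rate, assumed test counts and independent errors, and they vary about tenfold over the range shown.

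It is also fair to say that this is one secondary safety endpoint, that SAP Section 7.9 calls secondary p-values nominal, and that sites additionally confirm eligibility in a registry field. A single positive at entry is therefore not necessarily ignored. These points limit the severity but do not remove the inconsistency.

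**Conclusion.** The inconsistency holds on the text alone. Protocol Table 8 relies on the SAP for a confirmed definition, and the SAP's outcome row does not give one. As written, the row counts any positive test, any inhibitor recording or ITT alone, so findings that fall short of the SAP's own baseline inhibitor definition become events in a compared safety endpoint.

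The size cannot be derived from the documents. The illustration shows only that, under the stated assumptions, the choice of rule changes the share of falsely flagged participants by a factor of about 10 to 200 at 6 or 12 tests (for example 21.5% v 2.3%, and 1.2% v 0.006%). Bias between cohorts is a conditional risk: it needs more frequent testing in one cohort, which the documents suggest only as possible.

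This should be corrected before the SAP is finalised. It does not touch the primary analysis, the power or the sample size.

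**What to change.** - Reconcile the inhibitor row of SAP Table 5 with protocol Tables 4 and 8 by stating the rule there: two positive tests, or one positive test plus ITT.
- Align the short description in protocol Table 8 with the same rule when the protocol is next amended.
- List unconfirmed single positives descriptively by cohort, so that no possible signal is lost. Any comparison based on them should be a labelled sensitivity analysis.
- Report the number of inhibitor tests per participant by cohort, so that a difference in testing can be seen and taken into account.

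The cost is one SAP table row, one listing and one descriptive summary. The listing and the summary depend on individual test results and dates being in the data extract; SAP Table 5 already names the test date and titer fields. Protocol Section 10.3 has the SAP finalised before the data cut for the 18-month interim analysis, so the change fits the planned timeline.
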